## 7. PLANNED ANALYSIS

Safety analysis (refer to [Section 7.8](#)) will be performed by [REDACTED] and will be presented in Sections 15.1 to 15.4 of the CTR and in Appendix 16.2 and 16.1.13.1.

Inferential statistical analyses of PK endpoints (refer to [Section 7.4](#) and [Section 7.5.2](#)) will also be performed by [REDACTED] and will be presented in Section 15.5 of the CTR and in Appendix 16.1.13.3.

Descriptive data analysis of PK endpoints and concentrations will be performed by the [REDACTED] at [REDACTED] and will be presented in Section 15.6 of the CTR.

The format of the listings and tables will follow the BI standards (see BI-KMED-BDS-HTG-0045 ([7](#))) with the exception of those generated for PK-calculations following BI standards for PK/PD analysis ([8](#)).

The individual values of all subjects will be listed, sorted by treatment sequence, subject number and visit. The listings will be included in Appendix 16.2 of the CTR.

For end-of-text tables, the set of summary statistics for non-PK parameters is:

N	number of non-missing observations
Mean	arithmetic mean
SD	standard deviation
Min	minimum
Median	median
Max	maximum

For analyte concentrations, the following descriptive statistics will additionally be calculated:

CV	arithmetic coefficient of variation
gMean	geometric mean
gCV	geometric coefficient of variation

For PK parameters, the following descriptive statistics will additionally be calculated:

CV	arithmetic coefficient of variation
gMean	geometric mean
gCV	geometric coefficient of variation
P10	10 th percentile
Q1	1 st quartile
Q3	3 rd quartile
P90	90 th percentile

The data format for descriptive statistics of concentrations will be identical to the data format of the respective concentrations. The descriptive statistics of PK parameters will be calculated using the individual values with the number of decimal places as provided by the evaluation program. Then the individual values as well as the descriptive statistics will be reported with three significant digits in the CTR.

Tabulations of frequencies for categorical data will include all possible categories available in the eCRF, and will display the number of observations in a category, as well as the percentage (%). Percentages will be rounded to one decimal place and will be based on all subjects in the respective subject set whether they have non-missing values or not. The category 'missing' will be displayed only if there are actually missing values.

#### Exclusion of PK parameters

The ADS “ADPP” (PK parameters) contains column variables APEXC and APEXCO indicating inclusion/exclusion (APEXC) of a PK parameter and an analysis flag comment (APEXCO). All analyses based on the PKS will include parameters if they are not flagged for exclusion, that is APEXC is equal to “Included”.

#### Exclusion of PK concentrations

The ADS “ADPC” (PK concentrations per time-point or per time-interval) contains column variables ACEXC and ACEXCO indicating inclusion/exclusion (ACEXC) of a concentration and an analysis flag comment (ACEXCO). Exclusion of a concentration depends on the analysis flag comment ACEXCO. For example, if ACEXCO is set to ‘ALL CALC’, the value will be excluded for all types of analyses based on concentrations. If ACEXCO is set to ‘DESC STATS’ the value will be excluded from descriptive evaluations per planned time point/time interval. If ACEXCO contains the addition ‘TIME VIOLATION’ or ‘TIME DEVIATION’ the value can be used for further analyses based on actual times. If ACEXCO is set to ‘HALF LIFE’, the value will be excluded from half-life calculation (and, as a consequence, any calculation that relies on  $\lambda_z$ ) only; the value is included for all other analyses.

Further details are given in *BI-KMED-TMCP-MAN-0014* “Noncompartmental Pharmacokinetic / Pharmacodynamic Analyses of Clinical Studies” (6) and *BI-KMED-TMCP-MAN-0010*: “Description of Analytical Transfer Files and PK/PD Data Files” (9).

## **7.1 DEMOGRAPHIC AND OTHER BASELINE CHARACTERISTICS**

Only descriptive statistics are planned for this section of the report, based on the TS. The data will be summarised in total.

## **7.2 CONCOMITANT DISEASES AND MEDICATION**

Frequency tables are planned for this section of the report, based on the TS.

Concomitant diseases will be coded using the coding system of the Medical Dictionary for Drug Regulatory Activities (MedDRA). Medications will be coded using the World Health Organization Drug Dictionary (WHO DD). The coding version number will be displayed as a footnote in the respective output.

The diagnoses and medications will be listed. Subjects without any concomitant diagnoses or concomitant therapies should be marked with a “No” in the respective column.

The relevance of the concomitant therapies to the evaluation of PK will be decided no later than at the RPM.

## **7.3 TREATMENT COMPLIANCE**

**Section 4.3 of the CTP:** *Compliance will be assured by administration of all trial medication in the study centre under supervision of the investigating physician or a designee. The measured plasma concentrations of trial medication will provide additional confirmation of compliance.*

It is not intended to list the compliance separately. Any deviations from complete intake will be addressed in the RPM (see [Section 6.2](#)) and described in the CTR.

## **7.4 PRIMARY ENDPOINTS**

Relative bioavailability of BI 706321 in plasma is to be determined on the basis of the primary PK endpoints  $AUC_{0-\infty}$  and  $C_{max}$  (see [Section 5.1](#)).

### **7.4.1 Primary analysis of the primary endpoints**

#### **Section 7.3.1 of the CTP:**

*The statistical model used for the analysis of the primary endpoints will be an analysis of variance (ANOVA) model on the logarithmic scale. That is, the PK endpoints will be log-transformed (natural logarithm) prior to fitting the ANOVA model. This model will include effects accounting for the following sources of variation: subjects and treatment. The effect ‘subject’ will be considered as random, whereas ‘treatment’ will be considered as fixed. The model is described by the following equation:*

$$y_{km} = \mu + s_m + \tau_k + e_{km}, \text{ where}$$

*$y_{km}$  = logarithm of response measured on subject  $m$  receiving treatment  $k$ ,*

*$\mu$  = the overall mean,*

*$s_m$  = the effect associated with the  $m^{th}$  subject,  $m = 1, 2, \dots, n$*

$\tau_k$  = the  $k^{th}$  treatment effect,  $k = 1, 2,$

$e_{km}$  = the random error associated with the  $m^{th}$  subject who received treatment  $k$

[figure not shown]
where  $s_m \sim N(0, \sigma_B^2)$  i.i.d.,  $e_{km} \sim N(0, \sigma_W^2)$  i.i.d. and  $s_m, e_{km}$  are independent random variables.

Point estimates for the ratios of the geometric means (test/reference) for the primary endpoints (see CTP Section 2.1) and their two-sided 90% confidence intervals (CIs) will be provided.

For each endpoint, the difference between the expected means for  $\log(T)$ - $\log(R)$  will be estimated by the difference in the corresponding adjusted means (Least Squares Means). Additionally their two-sided 90% confidence intervals will be calculated based on the residual error from the ANOVA and quantiles from the  $t$ -distribution. These quantities will then be back-transformed to the original scale to provide the point estimate and 90% CIs for each endpoint.

The implementation for this analysis will be accomplished by using the CSD macros based on PKS. The following SAS code can be used:

```
PROC MIXED DATA=indata;
  CLASS subject treatment;
  MODEL logpk = treatment / DDFM=KR;
  RANDOM subject;
  LSMEANS treatment / PDIFF CL ALPHA=0.1;
  ESTIMATE 'T-R' treatment -1 1;
  RUN;
```

[figure not shown]

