7.2 NULL AND ALTERNATIVE HYPOTHESES

The relative bioavailability of BI 706321 given in combination with itraconazole (T) compared with BI 706321 given alone (R) will be estimated by the ratios of the geometric means (T/R), and their corresponding 2-sided 90% confidence intervals (CIs) will be provided. This method corresponds to the two one-sided t-test procedure, each at the 5% significance level. Since the main focus is on estimation and not testing, a formal hypothesis test and associated acceptance range is not specified.

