7.3.1 Primary endpoint analyses

Primary analyses

The statistical model used for the analysis of the primary endpoints will be an analysis of variance (ANOVA) model on the logarithmic scale. That is, the PK endpoints will be log-transformed (natural logarithm) prior to fitting the ANOVA model. This model will include effects accounting for the following sources of variation: subjects and treatment. The effect 'subjects' will be considered as random, whereas 'treatment' will be considered as fixed. The model is described by the following equation:

$$y_{km} = \mu + s_m + \tau_k + e_{km}, \text{ where}$$

Proprietary confidential information © 2021 Boehringer Ingelheim International GmbH or one or more of its affiliated companies

y_{km} = logarithm of response measured on subject m receiving treatment k,

μ = the overall mean,

s_m = the effect associated with the mth subject, m = 1, 2, ..., n

τ_k = the kth treatment effect, k = 1, 2

e_{km} = the random error associated with the mth subject who received treatment k

where $s_m \sim N(0, \sigma_B^2)$ i.i.d., $e_{km} \sim N(0, \sigma_W^2)$ i.i.d. and s_m, e_{km} are independent random variables.

Point estimates for the ratios of the geometric means (test/reference) for the primary endpoints (see Section 2.1) and their two-sided 90% confidence intervals (CIs) will be provided.

For each endpoint, the difference between the expected means for log(T)-log(R) will be estimated by the difference in the corresponding adjusted means (Least Squares Means). Additionally their two-sided 90% confidence intervals will be calculated based on the residual error from the ANOVA and quantiles from the t-distribution. These quantities will then be back-transformed to the original scale to provide the point estimate and 90% CIs for each endpoint.

[figure not shown]
Further exploratory analyses

The same statistical model as stated above will be repeated for the primary endpoints but with 'subjects' considered as fixed effects.

In addition to the model based approach all parameters will be calculated and analysed descriptively.

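### Does the SAP's example SAS code fail to give the 90% confidence interval for T/R?

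*SAP*

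**What the plan says.** Protocol 7.3.1, repeated in SAP 7.4.1, defines the primary result in words. The plan promises "Point estimates for the ratios of the geometric means (test/reference) for the primary endpoints" with two-sided 90% intervals. On direction, "the difference between the expected means for log(T)-log(R) will be estimated by the difference in the corresponding adjusted means". On scale, "These quantities will then be back-transformed to the original scale to provide the point estimate and 90% CIs for each endpoint". Protocol 7.2 also states the ratio as T/R, and on the level it says "This method corresponds to the two one-sided t-test procedure, each at the 5% significance level".

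SAP 7.4.1 assigns the implementation to the sponsor's standard macros and then gives SAS code as something the analyst may use. Its three relevant lines are:

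- the model, "MODEL logpk = treatment / DDFM=KR", with subject as a random effect;
- the adjusted means, "LSMEANS treatment / PDIFF CL ALPHA=0.1";
- the contrast, "ESTIMATE 'T-R' treatment -1 1".

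SAP 7.5.2 applies the same method to AUC0-tz, so the point touches both primary endpoints and the secondary one.

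**The concern.** The two statements point in opposite directions. `PDIFF` reports the first class level minus the second; coefficients of -1 and 1 give the second minus the first. The label T-R on the contrast is right only if R is level 1 and T is level 2. That is also how R and T, or the SAP's short labels BI and BI+ITZ, sort by default. So `PDIFF` gives R minus T, and it alone among the treatment differences carries 90% limits. The contrast line prints an estimate, standard error, degrees of freedom, t and p, but no limits.

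If someone exponentiated the printed limits as they stand, the report would show R/T. An increase in exposure would read as a decrease, in a trial whose protocol (section 1.4.2.4) considers an increase likely. If someone paired the contrast's estimate with the other statement's limits, the interval could exclude its own point estimate. Either slip would affect all three endpoints.

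**Working it through.** **1. Reproduce the planning figure.** The inputs come from Protocol 7.7: N = 12, gCV 25%, ratio 200%, and precision expected with 95% probability. For a paired design,

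ω = t(0.95, 11) × √(2 ln(1 + gCV²)/12) × √(χ²(0.95, 11)/11)

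= 1.7959 × √(2 × 0.060625/12) × √(19.675/11) = 1.7959 × 0.10052 × 1.3374 = 0.2414.

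exp(ω) = 1.2731, so the limits are 200/1.2731 = 157.10% and 200 × 1.2731 = 254.61%, as in Table 7.7: 1. All nine rows of that table reproduce to two decimals.

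**2. What the code would print for that row.** On the log scale, T minus R is 0.6931 with limits 0.4517 and 0.9346. The `PDIFF` output is -0.6931 with limits -0.9346 and -0.4517.

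| Handling of the printed limits | Ratio | 90% limits |
|---|---|---|
| Exponentiate as printed (R/T) | 50.0% | 39.3 to 63.7% |
| Negate, swap, exponentiate (T/R) | 200% | 157.10 to 254.61% |

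The first line is the reciprocal of the second: 1/2.5461 = 0.393 and 1/1.5710 = 0.637.

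**3. Is the recovery exact?** A contrast and its negative have the same variance. The Kenward-Roger degrees of freedom depend on the contrast only through quadratic terms, so they are the same too. Two numerical checks used simulated data, assuming gCV 25% and a true ratio of 2:

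- *Twelve complete pairs.* R minus T was -0.6779 (-0.8643 to -0.4915), or R/T 0.508 (0.421 to 0.612). Inversion gives T/R 1.970 (1.635 to 2.373), identical to the interval computed directly for T minus R.
- *Two subjects without the T period.* A REML mixed model gave +0.6563 or -0.6563 according to direction, with the same standard error of 0.1223. Incomplete pairs do not break the symmetry.

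**4. A second route from the same output.** The contrast line gives the estimate, standard error and degrees of freedom, so the 90% limits are estimate ± t(0.95, df) × SE. In the complete-pairs example the half-width is 0.8643 - 0.6779 = 0.1864, which is 1.7959 × 0.1038.

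**5. Text against code.** The code contains no exponentiation step. The analyst must already process the output under the written instructions, and those instructions state the direction, the ratio and the level. Orienting the difference belongs to that same step.

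**The case for a change.** The best case for a change is that the SAP's own introduction says it exists to give detailed procedures for executing the analysis, and this is its only explicit code for the primary endpoints. The two statements disagree in sign under any ordering of the levels: if T sorted first, `PDIFF` would be T minus R, but the line labelled T-R would then be R minus T. Under no ordering does the contrast line carry an interval. There is also a trap in a careless repair. Adding `CL` without `ALPHA=0.1` would give the default 95% interval, with a half-width 2.201/1.796 = 1.226 times as large on the log scale at 11 degrees of freedom. The full repair is one line and costs almost nothing.

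The reading of the code stands: it does not directly print the planned contrast with its planned interval. What does not follow is that the primary quantity is missing or wrong. To report R/T, an analyst would have to overlook the level labels in the differences output, the opposite-signed estimate labelled T-R a few lines away, and a definition of the ratio that both documents state. A positive estimate beside two negative limits is visibly inconsistent, and a reported fall in exposure would draw a query because the protocol expects a rise.

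**Conclusion.** No change is needed. Following the plan as written gives the correct T/R ratio and 90% interval for all three endpoints. The model, degrees-of-freedom method, confidence level and precision figures are unaffected. The 39.3 to 63.7% result is what a misreading would produce, not what the plan prescribes. Writing the contrast with both `CL` and `ALPHA=0.1` would be a convenience of display, with no gain in the result; dropping `PDIFF` would not help, since it supplies the adjusted-mean difference that the text describes.

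This rests on three assumptions: default ordering of the class levels (R before T), which the contrast coefficients imply but the documents do not state; the usual output rules of `PROC MIXED`; and macros that follow the written direction. The macros are not in the documents, so their output cannot be checked.

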## **7.5        SECONDARY ENDPOINTS**

### **7.5.1      Key secondary endpoint**

This section is not applicable as no key secondary endpoint has been specified in the protocol.

### **7.5.2      Other secondary endpoint**

The secondary PK parameter  $AUC_{0-tz}$  will be assessed using the same methods as described for the primary endpoints.

## **7.7        EXTENT OF EXPOSURE**

Descriptive statistics are planned for this section of the report based on the TS. The date and time of drug administration will be listed for each subject.

## **7.8        SAFETY ANALYSIS**

All safety analyses will be performed on the TS.

The safety data for treated subjects who failed to complete the study (dropouts or withdrawals) will be reported as far as their data are available. All withdrawals will be documented and the reason for withdrawal recorded.

## 7.8.1 Adverse Events

AEs will be coded with the most recent version of MedDRA.

Unless otherwise specified, the analyses of AEs will be descriptive in nature. All analyses of AEs will be based on the number of subjects with AEs and NOT on the number of AEs. BI standards as presented in “Analysis and Presentation of Adverse Event Data from Clinical Trials – Display Template” [BI-KMED-BDS-HTG-0041] ([10](#)) and [BI-KMED-BDS-HTG-0066] ([11](#)) will be applied.

The analysis of AEs will be based on the concept of treatment emergent AEs. That means that all AEs will be assigned to ‘screening’, ‘on-treatment’ or ‘follow-up’ phases as defined in [Section 6.1](#).

According to the clinical trial protocol, adverse events of special interest (AESI) will be analysed:

**Section 5.2.6.1.4 of the CTP:** *The following are considered as AESIs:*

- Hepatic injury  
*A hepatic injury is defined by the following alterations of hepatic laboratory parameters:*
  - o *An elevation of AST (aspartate transaminase) and/or ALT (alanine transaminase)  $\geq 3$ -fold ULN combined with an elevation of total bilirubin  $\geq 2$ -fold ULN measured in the same blood sample, or*
  - o *Aminotransferase (ALT, and/or AST) elevations  $\geq 10$  fold ULN*

According to ICH E3 ([12](#)), in addition to Deaths and Serious Adverse Events, ‘other significant’ AEs need to be listed in the clinical trial report. These will be any non-serious adverse event that led to an action taken with study drug (e.g., discontinuation or dose reduced or interrupted).

An overall summary of AEs will be presented.

The frequency of subjects with AEs will be summarised by treatment, primary system organ class (SOC) and preferred term (PT). Separate tables will be provided for subjects with serious AEs, for subjects with drug-related AEs, for subjects with drug-related serious adverse events and for subjects with AESIs. In addition, the frequency of subjects with AEs will be summarised by treatment, worst intensity, SOC and PT.

The SOCs and PTs will be sorted by frequency (within SOC). The MedDRA version number will be displayed as a footnote in the respective output.

In addition, frequencies of subjects with non-serious AEs that had an incidence of  $>5\%$  for at least one treatment will be summarised by treatment, primary SOC and PT.

For disclosure of adverse events on EudraCT, additional information not included in a standard AE analysis will be performed. The following three entries will be created:

- Adverse Events per arm for disclosure on EudraCT
- Non-serious Adverse Events for disclosure on EudraCT
- Serious Adverse Events for disclosure on EudraCT

## **7.8.2      Laboratory data**

The analyses of laboratory data will be descriptive in nature and will be based on BI standards [BI-KMED-BDS-HTG-0042] ([13](#)).

Laboratory data will be analysed qualitatively via comparison of laboratory data to their reference ranges. Values outside the reference range as well as values defined as possibly clinically significant will be flagged in the data listings.

Clinically relevant findings in laboratory data will be reported as baseline conditions (at screening) or as AEs (during the trial) if judged clinically relevant by the investigator, and will be analysed as such.

It is the investigator's responsibility to decide whether a lab value is clinically significantly abnormal or not (at the RPM at the latest).

Descriptive statistics of laboratory data including change from baseline will be calculated by planned time point based on the worst value of the subject at that planned time point (or assigned to that planned time point).

## **7.8.3      Vital signs**

Descriptive statistics over time including change from baseline will be performed for vital signs (body temperature, BP and PR). In the listing the difference from baseline will also be displayed.

For vital signs, descriptive statistics will be calculated by planned time point based on the last value of the subject at that planned time point (or assigned to that planned time point).

Clinically relevant findings in vital signs will be reported as AEs.

## **7.8.4      ECG**

ECG recordings will be checked by the investigator for pathological results. Clinically relevant abnormal findings for ECG will be listed under 'Relevant Medical History / Baseline Conditions' (when they occurred during screening) or will be reported as AEs (when they occurred during treatment), and will be analysed as such.

No separate ECG listing will be provided.

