5.2.4 Electrocardiogram

Twelve-lead ECGs (I, II, III, aVR, aVL, aVF, V1 - V6) will be recorded using a computerised electrocardiograph (CardioSoft EKG System, [REDACTED]
[REDACTED]) at the times provided in the [Flow Chart](#).

To achieve a stable heart rate at rest and to assure high quality recordings, the site personnel will be instructed to assure a relaxed and quiet environment, so that all subjects are at complete rest.

All ECGs will be recorded for a 10 sec duration after subjects have rested for at least 5 min in a supine position. ECG assessment will always precede all other study procedures scheduled for the same time to avoid compromising ECG quality.

All ECGs will be stored electronically on the Muse CV Cardiology System ([REDACTED]
[REDACTED]). Electrode placement will be performed according to the method of Wilson, Goldberger and Einthoven modified by Mason and Likar (hips and shoulders instead of ankles and wrists).

All locally printed ECGs will be evaluated by the investigator or a designee. Abnormal findings will be reported as AEs (during the trial) or baseline conditions (at screening) if assessed to be clinically relevant by the investigator. Any ECG abnormalities will be carefully monitored and, if necessary, the subject will be removed from the trial and will receive the appropriate medical treatment.

ECGs may be repeated for quality reasons (for instance, due to alternating current artefacts, muscle movements, or electrode dislocation) and the repeated ECG will be used for analysis. Additional (unscheduled) ECGs may be collected by the investigator for safety reasons.

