7.3.4 Safety analyses

Safety will be analysed based on the assessments described in Section 2.2.2.2. All treated subjects (TS, refer to Section 7.2) will be included in the safety analysis. Safety analyses will be descriptive in nature and based on BI standards. No hypothesis testing is planned.

Proprietary confidential information © 2021 Boehringer Ingelheim International GmbH or one or more of its affiliated companies

For all analyses, the treatment actually administered (= treatment at onset) to the subject will be used (any deviations from treatment will be discussed in the minutes of the Report Planning Meeting).

Treatments will be compared in a descriptive way. Tabulations of frequencies/proportions will be used to evaluate categorical (qualitative) data, and tabulations of descriptive statistics will be used to analyse continuous (quantitative) data.

Measurements (such as ECG, vital signs, or laboratory parameters) or AEs will be assigned to treatments (see Section [4.1](#)) based on the actual treatment at the planned time of the measurement or on the recorded time of AE onset (concept of treatment emergent AEs). Therefore, measurements planned or AEs recorded prior to first intake of trial medication will be assigned to the screening period, those between first trial medication intake and end of REP (see Section [1.2.3](#)) will be assigned to the treatment period. Events occurring after the REP but prior to next intake or end of trial termination date will be assigned to 'follow-up'. In case of two or more treatments, the follow-up will be summarized according to the previous treatment. These assignments including the corresponding time intervals will be defined in detail in the TSAP. Note that AEs occurring after the last per protocol contact but entered before final database lock will be reported to Pharmacovigilance only and will not be captured in the trial database.

Additionally, further treatment intervals (analysing treatments) may be defined in the TSAP in order to provide summary statistics for time intervals, such as combined treatments, on-treatment totals, or periods without treatment effects (such as screening and follow-up intervals).

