Adverse events will be coded using the Medical Dictionary for Regulatory Activities (MedDRA). Frequency, severity, and causal relationship of AEs will be tabulated by treatment, system organ class, and preferred term. SAEs, AESIs (see Section [5.2.6.1](#)), and other significant AEs (according to ICH E3) will be listed separately.

Previous and concomitant therapies will be presented per treatment group without consideration of time intervals and treatment periods.

Laboratory data will be compared to their reference ranges. Values outside the reference range as well as values defined as possibly clinically significant will be highlighted in the listings. Additionally, differences from baseline will be evaluated.

Vital signs or other safety-relevant data will be assessed with regard to possible on-treatment changes from baseline.

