#### **4. CHANGES IN THE PLANNED ANALYSIS OF THE STUDY**

All analyses as planned in the CTP will be performed and are described in more detail in this TSAP.

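### SAP 7.8.4 reports ECG only through investigator-judged findings, although the protocol plans a descriptive analysis of ECG measurements and SAP Section 4 declares no departure

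*SAP*

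**What the plan says.** **SAP.** Under 7.8.4, "ECG recordings will be checked by the investigator for pathological results". Clinically relevant abnormalities go to medical history or baseline conditions if found at screening; otherwise they "will be reported as AEs (when they occurred during treatment), and will be analysed as such". The section ends: "No separate ECG listing will be provided". It mentions no interval, summary statistic or change from baseline. SAP Section 4 states: "All analyses as planned in the CTP will be performed and are described in more detail in this TSAP".

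**Protocol.** Section 2.2.2.2 lists four safety items: adverse events, safety laboratory, 12-lead ECG and vital signs. Section 7.1 makes safety a further objective, to be evaluated by descriptive statistics for the parameters in Section 2.2.2. In Section 7.3.4:

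- "Safety will be analysed based on the assessments described in Section 2.2.2.2".
- "Measurements (such as ECG, vital signs, or laboratory parameters) or AEs will be assigned to treatments".
- Continuous data are to be tabulated with descriptive statistics.
- "Vital signs or other safety-relevant data will be assessed with regard to possible on-treatment changes from baseline".

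Section 5.2.4 says that ECGs may be repeated for quality reasons "and the repeated ECG will be used for analysis". It also says that abnormal ECGs become adverse events or baseline conditions if the investigator finds them clinically relevant. Section 5.6 says the schedule allows changes in ECG parameters to be monitored.

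**The concern.** The protocol treats ECG as a measurement to be described by treatment. The SAP treats it as a source of adverse events only, and does not record this as a change.

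The gap falls where ECG data are most informative. Protocol 1.4.2.4 expects BI 706321 concentrations and half-life to rise with itraconazole. The exclusion criteria in 3.3.3 cover QT-prolonging drugs, repeated QTc above 450 ms and risk factors for Torsade de Pointes, so the protocol itself regards QT as relevant. Reading single tracings for clinical relevance, in an open-label trial, is not designed to reveal a modest shift common to most subjects. Such a shift in PR, QRS or QTc would appear in no output that the available SAP text specifies.

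**Working it through.** No figure in the plan is in dispute. The check compares texts, followed by a short calculation of what an ECG table could show.

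**1. Treatment of each item listed in Protocol 2.2.2.2**

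| Item | Adverse-event route if clinically relevant | Descriptive statistics with change from baseline in SAP |
|---|---|---|
| Safety laboratory | Yes (Protocol 5.2.6.1.1, SAP 7.8.2) | Yes (SAP 7.8.2) |
| Vital signs | Yes (Protocol 5.2.6.1.1, SAP 7.8.3) | Yes (SAP 7.8.3) |
| 12-lead ECG | Yes (Protocol 5.2.4 and 5.2.6.1.1, SAP 7.8.4) | None specified |

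The fourth item, adverse events, includes physical-examination findings within it. ECG is listed separately from both, yet SAP 7.8.4 handles it much as SAP 7.8.5 handles physical examination. SAP 6.7 points the same way: its rule for unscheduled measurements names laboratory data and vital signs but not ECG.

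**2. Number of ECGs.** The flow chart schedules pre-dose, 4 h and 24 h in Period 1 (R), and pre-dose, 4 h and 46 h in Period 2 (T). That is 3 + 3 = 6 per subject, and 6 × 14 = 84 in 14 subjects, not counting screening and end of trial. Only 4 h is a post-dose time common to both periods.

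**3. Baseline.** SAP 6.7 defines baseline as the last measurement before BI 706321 in each period. In Period 2 the pre-dose ECG on Day 1 follows itraconazole on Days -3, -2 and -1, so change from it subtracts any effect of itraconazole alone. For laboratory data the SAP moves the Period 2 baseline to before the first itraconazole dose. That is not possible for ECG, because none is scheduled at that time. The Period 1 pre-dose ECG is the nearest scheduled reference without itraconazole.

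**4. Precision of a descriptive table.** The documents give no ECG variability. Assume a single-reading within-subject QTcF SD of 8 to 12 ms with independent errors, and 12 subjects (14 less the 2 allowed for in Protocol 7.7), so t(0.95, 11) = 1.796.

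- T-R difference at 4 h, each value corrected for its own period's pre-dose ECG (four readings): half-width = 1.796 × SD × sqrt(4/12) = 1.037 × SD, which is 8.3, 10.4 and 12.4 ms for SD 8, 10 and 12.
- Uncorrected T-R difference at 4 h (two readings): half-width = 1.796 × SD × sqrt(2/12) = 0.733 × SD, which is 5.9, 7.3 and 8.8 ms. Referring both periods to the Period 1 pre-dose ECG gives this same contrast, because the common baseline cancels. It keeps any itraconazole-alone effect, but also any drift between periods.

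**The case against.** The best defence is that Protocol 5.2.4, the section specific to ECG, prescribes the route the SAP follows: investigator review, then adverse event or baseline condition. On that view SAP 7.8.4 restates the protocol and nothing was dropped. The answer is in the table above. Protocol 5.2.6.1.1 sends laboratory and vital-sign changes through the same route, and the SAP still summarises both. The route is an addition to descriptive reporting, not a replacement for it.

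Other parts of the defence stand and limit the point. A reader might infer four stronger things that the documents do not support:

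- *That ECG effects would go unseen.* Protocol 5.2.4 has the locally printed ECGs evaluated, and clinically relevant findings reach the adverse-event tables by treatment.
- *That the protocol expressly promises ECG change from baseline.* The sentence in 7.3.4 names vital signs and other safety-relevant data, not ECG. Including ECG is a reasonable inference, because the other listed items are covered by name. The firmer basis is 7.1 and the rest of 7.3.4. The repeat-ECG sentence in 5.2.4 only settles which tracing counts.
- *That a heart-rate shift would be missed.* SAP 7.8.3 summarises pulse rate with change from baseline, and the flow chart schedules vital signs at the same treatment-period times as ECG.
- *That a table would make a 10 ms mean shift plainly visible.* For the baseline-corrected comparison, 10 ms lies inside the half-width at an SD of 10 or 12.

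The importance is also bounded. Protocol 1.2.1 reports no relevant ECG changes in the first-in-human trial, and 4.1.2 selects the dose to keep concentrations within the range already explored. Finally, the absence of a table is read from the SAP's silence; only a separate listing is expressly ruled out, and some SAP text is redacted.

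**Conclusion.** The point holds as an inconsistency between the protocol's safety analysis and SAP 7.8.4, not declared in SAP Section 4. Its consequence is limited to sub-clinical or average shifts in PR, QRS or QTc under treatment T. It does not touch the pharmacokinetic endpoints, and it is no evidence that a safety signal exists or would be concealed.

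The table would be descriptive. Its half-width of about 8 to 12 ms for a baseline-corrected T-R difference rests on the assumed SD of 8 to 12 ms, independent readings and 12 subjects. It could give context, or show a large common shift, but could not exclude a moderate one. The change is worth making because the recordings already exist and safety is a stated objective.

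**What to change.** In SAP 7.8.4, add a listing and descriptive statistics of PR, QRS and QTcF by treatment and planned time, with change from baseline. In the same section:

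- Show Period 2 values against both the Period 2 and the Period 1 pre-dose ECG, and say that the former follows three days of itraconazole.
- Treat only 4 h as a matched post-dose time; present 24 h (R) and 46 h (T) separately.
- Label the output descriptive, with no inference intended.

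The cost is one data export, one table and one listing, with no new recordings. Protocol 5.2.4 says that ECGs are stored electronically, but not that interval values are in the trial database, so the export must be confirmed first.

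If the intervals cannot be exported, state in SAP Section 4 that ECG is reported only through adverse events and baseline conditions, with the reason. That takes a sentence or two and removes the conflict with the no-change statement, but does not recover the lost information.
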